Materials and Methods: Women undergoing cesarean section will prospectively assigned to one of two groups. In the RM group, one minute after delivery, the investigators will apply RM: The ventilator will be switched to pressure control mode (from volume control) and the inspiratory time will be increased to 50%. The Positive End Expiratory Pressure (PEEP) will be increased up to 15cmH₂O and the Positive End Inspiratory Pressure (Ppeak) progressively will be increased up to 45cmH₂O. The whole RM will last 2 minutes. Then, volume control ventilation will be used again and PEEP step wise will be decreased to 8cmH₂O. Women in the RM group will be ventilated with low tidal volume after the RM (6 ml/kg). In the control group, the investigators will not use lung RM at all. Women in this group will be ventilated with higher tidal volume (8 ml/kg), which is a common tidal volume in everyday clinical practice. In both groups, lung compliance will be measured (dynamic compliance) as dv/dp (ml/cmH₂O). Measures will be assessed before RM but after delivery, 3 minutes after delivery and after recruitment, 10 and 20 minutes after recruitment. At all time points Ppeak, blood pressure, heart beats per minutes, oxygen saturation, end-tidal CO_2 and blood gas will also be measured too. In order to detect clinically meaningful differences, a power analysis will be conducted between the two study groups with regards to dynamic lung compliance (dv/dp), which is the primary outcome of the study. Women will be assigned to one of the two groups using computer-generated blocks.

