volume multiplied by ventilatory frequency) and expiratory tidal volume. In both groups of patients Com_{dyn} will be measured after delivery, but before RM (baseline measurement), and then 3, 10 and 20 minutes after the RM. At the same time points arterial blood pressure (systolic, diastolic and mean), heart rate, SpO₂, blood gas, ETCO₂, P_{peak}, expiratory tidal volume and minute volume will be measured too. SpO₂ and blood gas will be also measured postoperatively (10 minutes after extubation). Tables 2 and 3 present the basic patient's measurements. Data analysis example comes from preliminary data analysis before the beginning of the study.

Follow up measurements

Patients will be followed up for postoperative respiratory failure, which is defined as the need for non-invasive ventilation and/or mechanical ventilation after extubation. In cases of respiratory failure, the possible pulmonary complications are also being defined: pneumonia, atelectasis, pulmonary embolism, pneumothorax, acute lung injury (ALI), asthma, non-cardiogenic pulmonary oedema and severe hypercapnia. The routine postoperative oxygen use will also be noted and will be applied for half an hour postoperatively.

Statistical analysis

Before the beginning of the study, and for **determination of sample size**, we will conduct **power analysis**, in an attempt to estimate the sample size required so that the study would have adequate power to detect clinically meaningful differences between the two study groups with regards to lung compliance (dv/dp), which is the primary outcome of the study. For this analysis, we used the G*Power Software that is freely available online at <http://www.gpower.hhu.de/en.html> from the Psychology Department of the University of Dusseldorf, in Germany.

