Because of the higher inspiratory pressures during RM and PEEP used, the $P_{plateau}$ and P_{peak} are anticipated to be significantly higher in the RM group, compared with those in the control group, and this would be a possible serious safety issue, as high alveolar pressures could result in pneumothorax or/and barotrauma. As the study involves young and healthy population, the investigators believe that the above safety issues will not be a serious problem of the study. A second safety issue will be the hemodynamic instability during RM. Patients with serious hemodynamic instability will be removed from the study, as already mentioned.

End of treatment

The treatment (RM) will start after delivery (3 minutes) and will last until the end of the surgery. Specifically, in the RM group the RM will be performed 3 minutes after delivery but PEEP and low tidal volume (which are part of the whole RM technique) will be continued until the end of the operation.

End of Study

The patients will be monitored throughout the operation and in the postoperative period too (see also the measurements section-primary end point, secondary measurements and follow up). The follow up will last for all the length of hospital stay. The length of hospital stay will be recorded while all the adverse events that will be occurred during this period they will be recorded too. For this kind of population the hospital stay is usually short (<5 days).

Adverse events:

Hemodynamic instability during the RM will be the most important adverse event of the study. During the RM all women should be closely monitored for the occurrence of hypotension or the administration of a fluid bolus or vasopressor medication to support haemodynamic variables. Of course during the whole course of anesthesia the need for vasopressor should be monitored. Possible differences between the two groups should be mentioned for all the above parameters (table 1).

Postoperative lung complications (pneumonia, atelectasis, pulmonary embolism, pneumothorax, acute lung injury (ALI), asthma, non-cardiogenic pulmonary oedema and severe hypercapnia) should also be recorded. As we will mainly include young and healthy population serious lung complications and differences between groups are not anticipated.

Preliminary Data Results

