For safety issues we decided to perform a preliminary data analysis before the beginning of the study. We used 7 patients in each group, and we will use these data analysis as an example of our data presentation plan and to show the most important measurements of our study. At all time points (3, 10 and 20 minutes) after intervention there is a significant difference in Com_{dyn} between the two groups ($p < 0.001$). The Com_{dyn} is much higher in the RM group vs control group (table 2). The significant difference in lung Com_{dyn} depicts in figure 1a too.

Post intervention the peak inspiratory pressure at all time points (3, 10 and 20 minutes) is significantly lower in the RM group compared to control group ($p = 0.021$, table 2, figure 1b).

PO_2/F_iO_2 and PO_2 are also significantly higher in the RM group vs the control group ($p < 0.001$) at all time points post intervention (3, 10 and 20 minutes) while PO_2 is also significantly higher in the RM vs control group postoperatively ($p < 0.001$). SpO_2 is significantly difference between the two groups at 10 and 20 minutes post intervention and postoperatively ($p = 0.04$) – table 2

There are no significant differences in expiratory tidal volume, minute volume, end tidal CO_2 , PCO_2 and in hemodynamic data between the two groups (tables 2, 3).

[figure not shown]
Table 2. Respiratory Mechanics and Gas Exchange in the two groups of pregnant women (recruitment vs control, respectively-**Example**). Data are presented as mean \pm SD. The P-value corresponds to the tests of between subject main effects using the mixed Anova test (recruitment vs control group). The two groups were also compared separately at each time point using the independent two-sample t-test (*) and (**). (*) denotes significant differences from the control when $P < 0.01$ while (**) is used whenever $P < 0.05$. PaO₂, arterial blood oxygen; PaCO₂, arterial blood CO₂; SpO₂, arterial blood oxygen saturation; FiO₂, oxygen concentration.

	Baseline	After intervention (minutes)			Postoperative	P-value
		3 min	10 min	20 min		
Peak Inspiratory Pressure (cmH₂O)					-	0.021
Recruitment	23.9 (2.9)	19.9 (2.5)*	20.2 (2.9)*	20.3 (3.0)*		
Control	23.0 (2.8)	22.1 (2.8)	22.5 (2.7)	22.2 (2.7)		
Com_{dyn} (ml/cmH₂O)					-	<0.001
Recruitment	33.6 (6.8)	51.4 (12.8)*	49.9 (11.2)*	49.7 (10.9)*		
Control	31.1 (7.9)	29.6 (7.2)	30.6 (8.1)	30.9 (8.1)		
PaO₂ (mmHg)						<0.001
Recruitment	211.7 (10.6)	242.7 (26.9)*	242.1 (22.0)*	243.5 (27.6)*	108.4 (6.7)*	

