In our study we will check for differences in Com_{dyn} but not in the static compliance, which is also a very important record of the pulmonary performance. The reason is the lack of the special instruments. Many other records could be performed for respiratory mechanics too.

As we will use both RM and PEEP we will not be able to know if the compliance increasement (if exist) will be due to RM or to PEEP.

While this study will probably demonstrate a restoration in pulmonary compliance and in oxygenation, it will not be powered to describe pulmonary outcomes, such as postoperative atelectasis or pneumonia.

Appendix 1

Clinical Trial Methodology, [name]

Permuted blocks:

We consider a block of 10 patients and two treatments RM and Control. Then we define an array of 10 numbers, from 1 to 10:

1 2 3 4 5 6 7 8 9 10

A permutation of the array may produce the following blocks:

Block 1: 3 5 1 4 9 8 10 2 6 7

Block 2: 1 6 8 9 10 2 4 5 7 3

Block 9: 4 7 9 2 8 10 6 1 3 5

We need 9 blocks (90 patients)

We assign digits 1-5 to A

Digits 6-10 to B

Block	Sequence	Treatment	Patients
Block 1	3	A	1
	5	A	2
	1	A	3
	4	A	4
	9	B	5
	8	B	6
	10	B	7
	2	A	8
	6	B	9
	7	B	10
Block 2	1	A	11
	6	B	12
	8	B	13
	9	B	14
	10	B	15
	2	A	16
	4	A	17
	5	A	18
	7	B	19
	3	A	20
Block 3	3	A	21
	1	A	22
	7	B	23
	9	B	24
	2	A	25
	4	A	26
	10	B	27
	8	B	28
	5	A	29
	6	B	30

Διπλωματική Εργασία – [name]

Block 4	9	B	31
	3	A	32
	2	A	33
	10	B	34
	7	B	35
	1	A	36
	4	A	37
	8	B	38
	5	A	39
	6	B	40
Block 5	5	A	41
	1	A	42
	9	B	43
	7	B	44
	2	A	45
	10	B	46
	3	A	47
	4	A	48
	6	B	49
	8	B	50
Block 6	9	B	51
	1	A	52
	3	A	53
	7	B	54
	2	A	55
	4	A	56
	5	A	57
	8	B	58
	10	B	59
	6	B	60
Block 7	10	B	61
	5	A	62
	1	A	63
	8	B	64
	3	A	65
	2	A	66
	9	B	67
	4	A	68
	6	B	69
	7	B	70
Block 8	3	A	71
	8	B	72
	10	B	73
	1	A	74
	9	B	75
	2	A	76
	7	B	77
	6	B	78
	4	A	79
	5	A	80
Block 9	7	B	81
	1	A	82
	4	A	83
	8	B	84
	3	A	85
	10	B	86
	2	A	87
5	A	88	

	9	B	89
	6	B	90

Appendix 2

We will use power analysis – Two independent groups (comparison of means)-Clinical Trial Methodology, [name]

- Sample size in two independent groups.
- The formula for calculating the sample size is: $n \geq 2 \left(\frac{s}{\Delta} \right)^2 (1.96 + 1.28)^2$
- $S = SD$ (from previous trials it was found that the between subject variance of compliance is 25)
- $\Delta = 20$ (difference in compliance that is considered clinically significant)

Consequently,

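### The Protocol names raised P_plateau and P_peak as a barotrauma risk, but never measures P_plateau, takes no P_peak reading during the recruitment manoeuvre, and predicts P_peak in three incompatible ways

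*Protocol*

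**What the plan says.** **The safety statement.** The section Efficacy and Safety issues attributes higher airway pressures to the RM and to PEEP. It says that P_plateau and P_peak "are anticipated to be significantly higher in the RM group, compared with those in the control group", and that "this would be a possible serious safety issue, as high alveolar pressures could result in pneumothorax or/and barotrauma".

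**What is measured, and when.**
- The Abstract gives the schedule: "Measures will be assessed before RM but after delivery, 3 minutes after delivery and after recruitment, 10 and 20 minutes after recruitment".
- Secondary measurements has compliance "measured after delivery, but before RM (baseline measurement), and then 3, 10 and 20 minutes after the RM", and at the same times "ETCO₂, P_{peak}, expiratory tidal volume and minute volume will be measured too".
- Appendix 4 has one airway-pressure line, for peak pressure. Its columns are baseline, 3, 10 and 20 minutes, and postoperative.
- Under Blinding procedure, the blinded anaesthesiologist who records the monitor enters once the RM is over.
- Limitations of the study says that static compliance is not assessed: "The reason is the lack of the special instruments". The Introduction defines static compliance through the plateau pressure.

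**Other statements on P_peak.**
- The Abstract (Results and Discussion) expects no statistically or clinically significant group difference.
- Preliminary Data Results states that "the peak inspiratory pressure at all time points (3, 10 and 20 minutes) is significantly lower in the RM group" (p = 0.021). Study objectives repeats this in a paragraph that says the preliminary analysis was done for safety.

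**RM pressures.** The Abstract has P_peak up to 45 cmH2O with PEEP up to 15. Ventilatory Management has P_peak up to 45-50 cmH2O with PEEP stepped to 20.

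**The harm itself.** The Data Presentation Plan treats pneumothorax as a serious adverse event to be recorded. Table 1 has a row for it by arm, and follow-up lasts for the hospital stay.

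**The concern.** The Protocol identifies a mechanism of harm, high airway pressure, and two variables that express it. One is not collected. The other is collected just before and some minutes after the period in which the intervention raises it most. The readings that are taken can describe lung mechanics under the later ventilator settings, but not the pressure reached during the RM.

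Two things are at stake. If a pneumothorax occurs, no recorded pressure exists to set beside it, and the Protocol's differing targets cannot replace a recorded value. And with three different predictions for P_peak in one document, almost any result can be presented as expected.

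**Working it through.** **1. Variables named against variables collected.**

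| Variable in the safety statement | In a measurement list? | On Appendix 4? | Reading during the RM? |
|---|---|---|---|
| P_plateau | No | No | No |
| P_peak | Yes | Yes | No |

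**2. Direction of P_peak in the example data (Table 2, cmH2O).**

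| Time | RM | Control | RM minus control |
|---|---|---|---|
| Baseline | 23.9 | 23.0 | +0.9 |
| 3 min | 19.9 | 22.1 | -2.2 |
| 10 min | 20.2 | 22.5 | -2.3 |
| 20 min | 20.3 | 22.2 | -1.9 |

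The scheduled post-RM readings are thus 1.9 to 2.3 cmH2O lower with RM. The safety section predicts higher and the Abstract predicts no difference. Neither prediction is tied to a time point.

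**3. Does the stated p = 0.021 reproduce?** Preliminary Data Results gives 7 women per group. At 3 minutes the pooled variance is (2.5² + 2.8²)/2 = 7.045, so SD = 2.654. The standard error is 2.654 × √(2/7) = 1.419, and t = -2.2/1.419 = -1.55 on 12 df, p = 0.147. The same test gives p = 0.151 at 10 minutes and 0.237 at 20 minutes.

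Table 2 says that its p-value is the between-subject main effect. The mean difference over the four times is (0.9 - 2.2 - 2.3 - 1.9)/4 = -1.375. With an assumed within-woman correlation of 0 to 0.95 (not given in the Protocol), p runs from 0.09 to 0.37 at 7 per group. With the 40 and 41 women in the Table 3 caption, correlations of 0.8 to 0.9 give p = 0.018 to 0.024, which brackets 0.021. So the stated p-value does not reproduce at 7 per group. That is a separate inconsistency, and this point uses only the direction of the differences.

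**4. Size of the unrecorded interval.** The stated RM targets minus the post-intervention control means of 22.1 to 22.5 cmH2O give:
- smallest: 45 - 22.5 = 22.5 cmH2O
- largest: 50 - 22.1 = 27.9 cmH2O

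These are targets, not delivered pressures.

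**5. How much the pneumothorax count can carry.** With 0 events in n = 45, the one-sided 95% upper bound p solves (1 - p)^45 = 0.05. So p = 1 - 0.05^(1/45) = 0.064, or 6.4%. The Protocol gives no expected risk. If the true risk in the RM arm were 0.1%, the chance of seeing at least one case would be 1 - 0.999^45 = 4%. At 2% it would be 1 - 0.98^45 = 60%. Appendix 3, the form that feeds Table 1, has only a general field for pulmonary complications and no pneumothorax line.

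**The case against.** The strongest reply is that barotrauma is followed directly, through pneumothorax as a serious adverse event counted by arm. Pressure is only the mechanism, and in pressure-controlled mode with prescribed PEEP steps it is set by design, so recording it adds little. PEEP continues to the end of surgery, and the 3, 10 and 20 minute readings do cover that phase.

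Much of this stands. A reader might infer that barotrauma is not monitored, or that P_peak is read only after the RM. Neither is so: pneumothorax is tracked, and a baseline reading precedes the RM. A reader might also infer that the trial would declare the RM free of barotrauma because later P_peak is lower. The Protocol nowhere draws that conclusion, and the lower values are example data, not a trial result. Adding the initial 20 cmH2O to four 5 cmH2O PEEP steps gives a peak of 40, but no section states 40. Nor does the Limitations section say that plateau pressure cannot be measured; it speaks of static compliance, and the link is an inference through the Introduction's definition.

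The safety section may mean pressure during the RM. That would remove its conflict with Table 2, but the statement would then concern a quantity that nobody records. The Abstract's expectation of no difference would still conflict with the preliminary result.

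The argument that pressure is fixed by design fails on the Protocol's own text, because its sections disagree on peak pressure and on the PEEP ceiling. The pneumothorax count is too small to make exposure data unnecessary.

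**Conclusion.** The point holds in a limited form. The Protocol's safety statement names one variable that is never measured and one that is not read in the period of highest pressure, which by the stated targets is about 22.5 to 28 cmH2O above the control means. Its three statements on P_peak cannot all stand as written. The post-RM P_peak is a valid secondary measure of mechanics, but it cannot describe exposure during the RM. The size rests on two assumptions: that the targets are reached, and that trial control means resemble those in Table 2. The gap in recording and the conflicting predictions depend on neither. The primary analysis is unaffected. This is a change worth making to the safety data.

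**What to change.** 1. Add one Appendix 4 entry for the highest P_peak and highest PEEP reached during the RM, read from the monitor already in use. The unblinded investigator notes it on a separate sheet, kept from the blinded recorder and the blinded statistician.
2. Report it as a descriptive safety row, without a test between arms.
3. State that P_peak at 3, 10 and 20 minutes is a mechanics endpoint and not evidence on pressure exposure during the RM.
4. Remove P_plateau from the safety statement.
5. Reconcile the Abstract, Efficacy and Safety issues, and Preliminary Data Results on the expected direction of P_peak, naming the time to which each statement applies.
6. Reconcile the Abstract and Ventilatory Management on the RM's peak pressure and PEEP. Which setting is right is for the investigators; this review takes no position.

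The cost is one extra unblinded reading per woman, one form entry, one table row and some edits to the text. No visit, equipment or sample-size change follows.

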Results and Discussion: Data will be presented as mean value (+/- SD) while $p < 0.05$ will be considered significant. Mixed Analysis of Variance will be used for comparisons between and within group. There will be no significant difference in lung compliance between groups before RM ($p > 0.05$). Two-sample t-test to compare the two groups at each time point will be used as supplementary analysis, while chi-square test for categorical variables and two-sample t-test for continuous variables for patient and procedural characteristics differences between the two groups, will be used. In the RM group, according to similar studies, the investigators are expecting to see a significant increase in lung compliance after RM compared to control group were RM was not applied. In the RM group the investigators estimate that dynamic lung compliance will be significantly higher at all time points (3 minutes, 10 and 20 minutes) compared to baseline compliance or compliance before RM too. In the control group there should be no significant difference in dynamic lung compliance at the different time points. There should be no significant demographic differences between groups while the investigators estimate that there will be no statistical or/and clinical significant differences in SpO_2 , blood gas, end-tidal CO_2 , Ppeak, and women hemodynamic.

Introduction

General anesthesia (GA) can cause changes in respiratory mechanics and lung function, which persist for days after surgery. These changes occur immediately after induction of anesthesia but are aggravated with mechanical ventilation¹⁻⁵. The reduction in lung compliance and the formation of atelectasis after the induction of GA is a significant cause of abnormalities in regional ventilation and gas exchange⁴. Two different types of atelectasis, compression atelectasis and resorption atelectasis, have an impact on patient's condition. The reduced activity of the diaphragm and the weight of lung or abdominal organs in the supine position promote the formation of compression atelectasis.

Atelectasis formation

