Our power analysis is based on previous studies but is even more generous^{17,22}. The required sample size calculation was based on the following assumptions: Clinically meaningful difference between the two groups is 20% of the mean value, and SD of the observed lung compliance is 25% of the mean value (rather generous), therefore size effect $d = 20\% / 25\% = 0.8$, with two-sided testing, with $\alpha = 0.05$ and $b = 0.1$ (therefore, power = $1 - b = 0.9$). Under these assumptions, G*Power indicated that we will need minimum 34 patients per group for this study to have adequate power. To confirm accuracy of this calculation, we will also conduct sample size estimation using the Statistica v 7.0 Statistical Software package (StatSoft Inc, Tulsa, Oklahome, USA), in order to find out if this confirmatory analysis will produce identical results. Finally we will confirm our results using the suitable mathematic formula (see [appendix 2](#)).

In order to allow for possible protocol violations, errors, patient attrition or other study shortcomings, we will enroll 45 patients in each arm of the study (about 10 women more in each group of patients). As pregnant women are a very “sensitive” population and we are afraid of much protocol violation (removal women from protocol mainly due to hemodynamic instability) we will chose to randomize 45 women per group, which is a generous number.

We will check if data are normally distributed (Kolmogorov Smirnov and Shapiro Wilks test). Ventilatory and haemodynamic data and intraoperative and postoperative variables (all continuous variables) will be presented as mean values (+/- SD). Data will be compared between and within groups using Mixed Analysis of Variance (Mixed Anova-General Linear Model) if are normally distributed or with Kruskal Wallis test in case that we do not have normally distributed data.

Bonferoni correction will be used for multiple comparisons correction. In order to check and supplement our Mixed Analysis of Variance we will also use two-sample t-test to compare the two groups at each time point (for ventilatory and haemodynamic variables). Patient and procedural characteristics will be compared between groups using chi-square test for categorical variables and independent-sample t-test for continuous variables. Two tailed P-values <0.05 will be considered statistically significant. For data analysis SPSS statistical software version 22 will be used.

Patients Records

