Control	214 (18.4)	219.8 (22.6)	214 (22.3)	212 (38.4)	98.4 (5.3)	
PaO₂/FiO₂					-	<0.001
Recruitment	422.2 (22.1)	481.1 (48.6)*	475.3 (42.7)*	474 (50.3)*		
Control	426.4 (43.3)	429 (39.2)	426 (41.5)	422.5 (37.5)		
ET_{CO2} (mmHg)					-	0.5
Recruitment	30.9 (3.4)	29.2 (3.4)	28.4 (3.8)	28.1 (3.6)		
Control	30.4 (2.9)	30.0 (3.0)	29.4 (2.8)	28.6 (2.7)		
Expiratory Tidal Volume (ml)						0.5
Recruitment	584.5 (63.1)	588 (65.3)	578 (66.2)	581 (65.1)	576 (62.8)	
Control	575.9 (54.2)	582 (66.3)	585 (58.4)	579 (66.3)	585 (64.8)	
Minute Volume (lit)						0.38
Recruitment	7.0 (7.74)	7.1 (0.63)	6.9 (0.65)	7.1 (0.68)	6.9 (0.65)	
Control	6.8 (0.63)	6.9(0.67)	6.8 (0.72)	7.1 (0.65)	6.8 (0.59)	
PCO₂ (mmHg)						0.08
Recruitment	33.9 (2.2)	32.7 (3.0)	32.7(3.8)	32.7 (3.7)	35.6 (1.9)**	
Control	34.4 (1.9)	33.7 (2.9)	33.8 (2.9)	33.6 (3.2)	36.5 (1.4)**	
SpO₂						0.04
Recruitment	98.8 (0.7)	99 (0.7)	99.1 (0.8)**	98.9 (0.8)**	98.3 (0.8)*	
Control	99 (0.7)	98.9 (0.7)	98.7 (0.6)	98.6 (0.5)	97.7 (0.7)	

Table 3. Systolic Arterial Pressure, Diastolic Arterial Pressure, Mean Arterial Pressure and Heart rate between the two groups of pregnant women (recruitment vs control, n=40 and n=41 respectively- **Example**). Data are presented as mean \pm SD. The P-value corresponds to the tests of between subject main effects using the mixed Anova test (recruitment vs control group). The two groups were also compared separately at each time point using the independent two-sample t-test.

	Baseline	After Intervention (minutes)			P- Value
		3 min	10 min	20 min	
Systolic Arterial Pressure (mmHg)					0.63
Recruitment Control	124.5 (6.2) 125.7 (9.1)	121.8 (8.4) 122.7 (9.5)	122.8 (9.8) 120.1 (10.7)	121.9 (10) 119.2 (10.5)	
Diastolic Arterial Pressure (mmHg)					0.8
Recruitment Control	73.6 (10.5) 72.7 (8.0)	70.5 (10.0) 70.6 (7.6)	70.3 (9.6) 71.1 (7.6)	69.6 (9.0) 71.1 (6.3)	
Mean Arterial Pressure (mmHg)					0.98
Recruitment Control	88.8 (10.20) 88.4 (9.50)	83.4 (10.1) 85.8 (7.4)	84.4 (10.3) 83.8 (7.2)	83.8 (10.3) 82.4 (7.2)	
Heart Rate (beats per minute)					0.96
Recruitment Control	95.1 (12.3) 96.2 (6.7)	92.5 (12.4) 91.6 (6.2)	91.6 (11.6) 91.5 (6.6)	91.4 (12.0) 91.0 (7.0)	

Figure 1a and 1b: RM=recruitment maneuver group, Baseline=before intervention, 3, 10 and 20 minutes=post intervention time.

Difference in Peak Inspiratory Pressure between the two groups

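### The haemodynamic summary rests on one main-effect P-value that averages in the pre-manoeuvre baseline, so a short fall in pressure after the manoeuvre is diluted or cancelled, and no difference or interval is shown

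*Protocol*

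**What the plan says.** The Brief Description labels the trial a safety and efficacy study, and the Adverse events section ranks haemodynamic instability during the manoeuvre as the most important adverse event.

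Preliminary Data Results opens with "For safety issues we decided to perform a preliminary data analysis before the beginning of the study". It gives the size as "We used 7 patients in each group" and offers the analysis as the example of how trial data will be presented. Its haemodynamic result is one sentence. It begins "There are no significant differences in expiratory tidal volume, minute volume" and, after two gas-exchange variables, ends "and in hemodynamic data between the two groups (tables 2, 3").

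The Table 3 legend identifies the P-value shown: "The P-value corresponds to the tests of between subject main effects using the mixed Anova test (recruitment vs control group"). The values are 0.63 (systolic), 0.8 (diastolic), 0.98 (MAP) and 0.96 (heart rate). The legend gives group sizes of 40 and 41 and adds that the groups were also compared at each time point by two-sample t-test.

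Statistical analysis plans the same pair of methods for the trial: mixed ANOVA, supplemented by t-tests at each time point for ventilatory and haemodynamic variables. It adds "Two tailed P-values <0.05 will be considered statistically significant" and "Bonferoni correction will be used for multiple comparisons correction", without naming the family of comparisons. The Abstract anticipates the outcome: "the investigators estimate that there will be no statistical or/and clinical significant differences in" a list that includes haemodynamics.

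**The concern.** A between-subject main effect compares the groups on each woman's average over baseline, 3, 10 and 20 minutes. The baseline reading precedes the manoeuvre and can carry no effect of it. A fall confined to the first minutes enters the average at one quarter of its size, and small opposite differences at the other times can cancel it. The haemodynamic effect of interest here is the one just after the manoeuvre, which this test is least able to see.

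The summary then gives only significance status. Without a difference and an interval, a reader cannot tell a small effect measured well from an effect of unknown size measured badly. If the trial is reported in this format, it could appear to show no haemodynamic effect when its data cannot exclude a fall that matters.

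**Working it through.** **Inputs from the protocol.** Two-sided alpha 0.05 and 45 women per group (Statistical analysis). Table 3 MAP, mean (SD), at baseline, 3, 10 and 20 minutes:
- RM: 88.8 (10.2), 83.4 (10.1), 84.4 (10.3), 83.8 (10.3)
- Control: 88.4 (9.5), 85.8 (7.4), 83.8 (7.2), 82.4 (7.2)

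**Assumptions.** The protocol defines no relevant pressure difference, so 0.5 SD is used as an illustration. Within-woman correlation rho is taken as 0.5 to 0.9, with equal SDs and equal correlations across times.

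**1. Where P = 0.98 comes from.**
- RM: (88.8 + 83.4 + 84.4 + 83.8)/4 = 85.1
- Control: (88.4 + 85.8 + 83.8 + 82.4)/4 = 85.1

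The averages agree to the precision printed, so a main-effect P close to 1 follows. By time, RM minus control is +0.4, -2.4, +0.6 and +1.4 mmHg, which sums to zero. The fall from baseline to 3 minutes is 5.4 mmHg with RM and 2.6 with control, a difference of 2.8.

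**2. What the 3-minute data can exclude.** The interval is -2.4 ± t × s × sqrt(1/n1 + 1/n2), where s is the pooled SD.
- n = 7 and 7: s = 8.85, SE = 4.73, t = 2.179, 95% CI -12.7 to +7.9 (P = 0.62)
- n = 40 and 41: s = 8.84, SE = 1.96, t = 1.990, 95% CI -6.3 to +1.5 (P = 0.23)

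Half an SD is about 4.4 mmHg. Neither interval excludes a drop of that size.

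**3. Chance of missing a 0.5-SD drop with the time-point t-test** (noncentral t):
- 45 per group: 35%, or 52% if Bonferroni is applied over three times
- 40 and 41: 40%
- 7 per group: 86%

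**4. The same with the main effect, 45 per group.** The SD of a four-reading mean is SD × sqrt((1 + 3rho)/4), that is 0.79 SD at rho = 0.5 and 0.96 SD at rho = 0.9.
- Drop at 3 minutes only: the mean shifts by 0.5/4 = 0.125 SD. The standardised effect is 0.158 to 0.130, and 88% to 91% are missed.
- Drop at 3, 10 and 20 minutes: the mean shifts by 0.375 SD. The standardised effect is 0.474 to 0.390, and 40% to 55% are missed.

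**5. With baseline adjustment at 3 minutes, 45 per group.** The residual SD is SD × sqrt(1 - rho²), that is 0.866 SD at rho = 0.5 and 0.714 SD at rho = 0.7. About 23% and 9% are missed, against 35% unadjusted. The adjusted interval itself needs individual data and cannot be computed from Table 3.

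**6. The sample size behind the example.** Table 2 stars P_peak at 3 minutes as P < 0.01: 19.9 (2.5) against 22.1 (2.8). A t-test on these figures gives P = 0.15 with 7 per group and P = 0.0004 with 40 and 41. The star fits 40 and 41, not the 7 per group in the text.

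**The case against.** The strongest reply is that the main effect is not the whole plan. Statistical analysis and the Table 3 legend both provide t-tests at each time point for haemodynamic variables, and a 3-minute fall would be examined there. This stands: the 88-91% figure describes the headline P-value, not everything the trial will compute. The time-point test still misses the assumed drop 35% of the time, and its results reach the reader only as significant or not.

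A reader might infer that the protocol treats P > 0.05 as proof of haemodynamic safety. It does not say so. The sentence in Preliminary Data Results describes example data, and the Abstract states an expectation. Safety is also followed through events: the Adverse events section asks for group differences in hypotension, fluid boluses and vasopressor use, and Table 1 lists ephedrine, crystalloids and colloids by group. That softens the concern but does not replace the pressure comparison. Table 1 has no row for hypotension, the scheduled readings do not fall during the manoeuvre, and removal of unstable women pulls the remaining readings towards no difference.

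The 0.5 SD is also open to challenge, since it is a reviewer's choice. With an SD of 8.85, a 10 mmHg difference at one time would be detected with power above 99% at 45 per group, and the 95% CI half-width would be about 3.7 mmHg. So the trial can be informative about pressure, provided that the intervals are shown.

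Finally, a margin is something a separate analysis plan may hold. That is accepted, and the point does not depend on one.

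**Conclusion.** The point holds as one about the choice and presentation of the haemodynamic comparison. The headline P-value includes a reading that the manoeuvre cannot have affected and averages out a short effect. The protocol's own MAP data show this: P = 0.98 beside a 2.4 mmHg lower RM mean at 3 minutes, with an interval reaching -12.7 or -6.3 mmHg depending on which sample size is true. The 0.98 reflects cancellation across times and is not evidence that pressure was unaffected at 3 minutes.

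The miss rates depend on the assumed 0.5 SD, and those for the main effect and the adjusted analysis also on the assumed correlations. The 35% and the 88-91% belong to different tests and should not be merged into one range. The 86% applies only to the 7-per-group example. The documents do not support the stronger claim that significance testing is the trial's only safeguard on haemodynamics.

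**What to change.** For MAP, systolic pressure, diastolic pressure and heart rate:
- Report the RM-minus-control difference at 3, 10 and 20 minutes, with the 3-minute result first, adjusted for the baseline reading and with its 95% CI. Show this in place of the four-reading main-effect P.
- State that a non-significant result will not be described as absence of a haemodynamic effect. If an interval is too wide to settle the matter, say that the result is inconclusive.
- In Preliminary Data Results, replace the haemodynamic part of the sentence with the differences and intervals, and do not cite that analysis as safety evidence.
- Reconcile its sample size: 7 per group in the text, 40 and 41 in the Table 3 legend.

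A formal margin is optional and may be left to the statistical analysis plan. The cost is a short change of wording and a few intervals from readings already scheduled. The drawback is that the haemodynamic statement may have to read as inconclusive.
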